#### 5.2.1 *Target Lesions*

Diminutive ( $\leq 5\text{mm}$ ) colorectal polyps identified during colonoscopy will be considered target lesions.

### 5.3 *Justification for the Study Design*

This study design was chosen to follow current standard of care endoscopy procedures with the exception of introduction of CDSD as part of the physician's decision algorithm. Pathology remains the gold standard methodology for diagnosis in this study. The study aims to demonstrate that CDSD is capable of increasing the sensitivity and specificity of endoscopist predictions for diminutive polyp histology. The single arm design was chosen to evaluate the incremental improvement in predictive accuracy relative to the standard of care while controlling for variability in polyp presentation by using a matched pair design. Inclusion of endoscopists comprising a range of experience is intended to reflect real-life clinical practice and potential increased benefit to non-expert users. Blinding allows for independence of assessments, and comparison of results without bias.

## 6 **Subject Selection**

### 6.1 *Study Population and Eligibility*

Subjects who provide informed consent and meet all of the inclusion criteria and none of the exclusion criteria will be enrolled in this study.

### 6.2 *Entrance Criteria*

#### 6.2.1 **Inclusion Criteria**

Subjects who meet all of the following criteria may be given consideration for inclusion in this clinical study, provided no exclusion criterion is met.

1.  $\geq 18$  years of age
2. Willing and able to provide informed consent
3. Subject scheduled for colonoscopy

#### 6.2.2 **Exclusion Criteria**

Subjects who meet any one of the following criteria will be excluded from this clinical study.

1. Polyposis syndromes including Familial Adenomatous Polyposis (FAP) Syndrome
2. Inflammatory Bowel Disease (IBD)
3. Hereditary Non Polyposis Colorectal Cancer (HNPCC)
4. Severe coagulopathy
5. Subjects with a cumulative score of 6 or less on the Boston Bowel Prep Score
6. No diminutive polyps detected during colonoscopy

## 7 Subject Accountability

### 7.1 *Point of Enrollment*

Existing family history and other standard-of-care screening tests and questions may be used to determine subject eligibility for recruitment prior to the colonoscopy procedure. Following signing of the informed consent form (ICF), subjects will be defined as being enrolled in the study, however; subjects may subsequently be excluded from the study based on findings during the procedure consistent with exclusion criteria listed in Section 6. Consented subjects who fail the procedural entrance criteria will be considered screening failures, and the reason for exclusion will be recorded. Subjects who meet all entrance criteria including those evaluated during the colonoscopy procedure will be considered the Intent to Treat (ITT) population for this study.

## 8 Study Methods

### 8.1 *Data Collection*

**Table 8-1: Data Collection Schedule**

Procedure/Assessment	Screening / Enrollment	Procedure	Post- procedure (Lab results only)
Informed consent	X		
Inclusion / Exclusion	X	X	
Demographics	X		
Medical history	X		
Colonoscopy / CDSD		X	
Pathology assessment			X
Follow-up pathology assessment			X (as needed)
Device deficiencies assessment		X	

X: Required Procedure/Assessment

### 8.2 *Informed Consent*

All subjects taking part in this clinical study must undergo the informed consent process. Subjects must be allowed adequate time to review the consent, raise questions, and make a voluntary decision to participate in the clinical study. Each subject must sign and date the IRB approved ICF before any clinical study-related procedures are performed. A copy of signed ICF will be provided to the subject for his/her records. A subject's participation in the clinical study begins with the signing and dating of the ICF.

### 8.2.1 Post-Consent Eligibility Validation

Exclusion criteria such as poor bowel prep and absence of diminutive polyps will not be known until after the start of the procedure. Consented subjects who fail exclusion criteria during the procedure will be considered screening failures and excluded from the statistical analysis.

### 8.3 Screening/Enrollment

Consecutive subjects presenting for colonoscopy will be considered for participation. Existing family history and other standard-of-care screening tests and questions may be used to determine subject eligibility for recruitment prior to the colonoscopy procedure. Subjects meeting the pre-procedural entrance criteria will be consented prior to the colonoscopy procedure. Demographic and relevant medical history data will be collected. Subjects may still be excluded from the study during the colonoscopy procedure assessment if they no longer meet entrance criteria.

### 8.4 Colonoscopy Procedure

The colonoscopy procedure will proceed as per standard of care with the exception of use of CDSD. The following information will be collected during this visit:

- Colonoscopy indication
- Endoscopist
- Colonoscope model used
- Procedure date
- Length of procedure (scope in to scope out) including cecal intubation time and withdrawal time
- Procedural entrance criteria
- Unaided physician prediction using white light
- Unaided physician prediction and confidence level using NBI
- CDSD prediction
- CDSD aided physician prediction and confidence level
- Number, size, shape and location of all identified polyps

### 8.5 Post-Procedure

Lab results will be collected for all specimens sent to pathology, including secondary lab results in cases where a recut/re-analysis of specimen is requested by the endoscopist and

performed. Diagnosis based on pathology will be recorded as well as prescribed surveillance interval.

### 8.6 *Study Completion*

An individual subject's participation in the study shall conclude following the end of the procedure. Data collection shall end following review of the pathology report for any specimens resected or biopsied during the procedure. In cases where pathology re-evaluation is requested, data collection shall end once all subsequent pathology re-evaluations are complete and secondary pathology reports are reviewed by the investigators.

### 8.7 *Source Documents*

Source documents are the subject records maintained at the study site. In most cases, the source documents will be the physician's or hospital's subject chart. In some cases, the source documents may be electronic. In both cases, the information captured in the CRF must match the information in the chart or electronic source document. The Investigator agrees to make source documents (hard copy or electronic) available for monitoring by the Sponsor and/or their representatives.

### 8.8 *Local Laboratory Documentation*

Local laboratories for the clinical sites will be used as per standard practice. Appropriate certifications and documentation records will be collected for the study file.

## 9 Statistical Considerations

### 9.1 *Endpoints*

#### 9.1.1 *Primary Endpoint*

The co-primary effectiveness endpoint is the sensitivity and specificity of CDSD-aided endoscopist prediction.

$$\text{Sensitivity (Sn)} = \frac{TP}{TP + FN} \quad \text{Specificity (Sp)} = \frac{TN}{TN + FP}$$

#### 9.1.1.1 Hypotheses

A 2x2 table for accuracy of paired predictions with NBI is constructed for both adenomas (Sn, histology reference standard positive) and non-adenomas (Sp, histology reference standard negative) (Tables 9-1 and 9-2).

**Table 9-1: Sample 2x2 Table for Paired Adenoma Predictions with NBI (Reference Standard Positive)**

		CDSD-unaided Prediction		Total
		Positive	Negative	
CDSD-aided Prediction	Positive	a	b	a+b
	Negative	c	d	c+d
	Total	a+c	b+d	a+b+c+d

**Table 9-2: Sample 2x2 Table for Paired Non-Adenoma Predictions with NBI (Reference Standard Negative)**

		CDSD-unaided Prediction		Total
		Positive	Negative	
CDSD-aided Prediction	Positive	m	n	m+n
	Negative	p	q	p+q
	Total	m+p	n+q	m+n+p+q

In order to test the effect of CDSD, individual hypotheses for sensitivity and specificity will be evaluated based on 2x2 tables of paired predictions for adenomas and non-adenomas, respectively. The hypothesis for Sensitivity is:

$$H_0 S_n: S_n \text{ CDSD-aided} \leq S_n \text{ CDSD-unaided} \text{ or } \frac{(a+b)}{(a+b+c+d)} \leq \frac{(a+c)}{(a+b+c+d)}$$

$$H_1 S_n: S_n \text{ CDSD-aided} > S_n \text{ CDSD-unaided} \text{ or } \frac{(a+b)}{(a+b+c+d)} > \frac{(a+c)}{(a+b+c+d)}$$

The hypothesis for Specificity is:

$$H_0 S_p: S_p \text{ CDSD-aided} \leq S_p \text{ CDSD-unaided} \text{ or } \frac{(p+q)}{(m+n+p+q)} \leq \frac{(n+q)}{(m+n+p+q)}$$

$$H_1 S_p: S_p \text{ CDSD-aided} > S_p \text{ CDSD-unaided} \text{ or } \frac{(p+q)}{(m+n+p+q)} > \frac{(n+q)}{(m+n+p+q)}$$

The overall hypothesis tested is that the CDSD-aided endoscopist predictions of polyp histology will have superior sensitivity and specificity as compared with the unaided endoscopist predictions of histology on the same polyps.

$H_0: H_{0Sn}$  or  $H_{0Sp}$

$H_1: H_{1Sn}$  and  $H_{1Sp}$

#### 9.1.1.2 Sample Size

In order to demonstrate the primary endpoint with 80% power and one-sided significance level of 2.5% a minimum of 40 endoscopists and approximately 2400 subjects are required. Assuming 85% of subjects have adequate bowel preparation, 52% of subjects with adequate bowel preparation have one or more diminutive polyps, 1.81 diminutive polyps per subject having at least one diminutive polyp and a 58% adenoma prevalence yields a minimum requirement of 1918 polyps.

#### 9.1.1.3 Statistical Methods

The 95% confidence intervals for the differences between CDSD-aided and CDSD-unaided sensitivity and specificity are estimated using bootstrap resampling with resampling performed first at the endoscopist level and then at the patient level. The null hypothesis is rejected if both lower bounds of the confidence intervals are greater than 0.

$$Sn_{CDSD\text{-aided}} - Sn_{CDSD\text{-unaided}} > 0$$

$$Sp_{CDSD\text{-aided}} - Sp_{CDSD\text{-unaided}} > 0$$

The assumptions of the statistical model used to establish the sample size are:

1. There are at a minimum 40 endoscopists participating in the study and each endoscopist makes approximately 60 predictions,
2. For each endoscope (CF-HQ190 and PCF-H190) and for each class of diminutive polyp (adenoma and non-adenoma) there is an intra-cluster correlation coefficient of 0.05 for predictions made by the same endoscopist,
3. There is no correlation between an operator's sensitivity and specificity,
4. There is no correlation between predictions made by the same operator across endoscope models (CF-HQ190 and PCF-H190),
5. The distribution of adenomas and non-adenomas within subjects with more than one diminutive polyp was modelled and is described in the statistical analysis plan,
6. The values from the range of possible values for the discordant pairs (b, c, n and p) that are used to calculate sample size are reported in Tables 9-3, 9-4, 9-5 and 9-6),
7. Without CDSD, the operator sensitivity is presumed to be 88% and the specificity is presumed to be 58% across all operators for all colonoscopes. The operator sensitivity with CDSD is presumed to be 92% and specificity with CDSD is presumed to be 75% across all operators when using the CF-HQ190 colonoscope (benchtop testing data). The operator sensitivity with CDSD is presumed to be 91% and the specificity with CDSD is presumed to be 72% across all operators when using the PCF-H190 colonoscope (benchtop testing data). Combined, the operator

sensitivity with CDSD is presumed to be 92% and the specificity with CDSD is presumed to be 73% across all operators,

8. The prediction rate for CDSD with CF-HQ190 is 89% and the prediction rate for CDSD with the PCF-H190 is 84% (benchtop testing data),
9. The proportion of subjects examined with the PCF-H190 will be 50%,
10. The proportion of subjects that present with adequate bowel preparation will be 85%, the proportion of patients with diminutive polyps will be 52%, there will be 1.81 diminutive polyps per subject having diminutive polyps, the overall prevalence of adenomas will be 58%,
11. The proportion of predictions with and without CDSD that will be assessed as normal tissue by pathology is estimated to be approximately 15%.

A simulation analysis was performed in which a dataset is generated at each step following the assumptions above. To account for intra-cluster correlation at the endoscopist level, for each endoscope and each class of diminutive polyps, the proportions of accurate and non-accurate predictions are sampled following a Dirichlet distribution, as described in Gönen. At each simulation step, bootstrap resampling based 95% confidence intervals for the differences between CDSD-aided and CDSD-unaided sensitivity and specificity are calculated. Bootstrap resampling is performed first at the endoscopist level and then at the patient level. The power is calculated as the number of simulation steps where the lower bound of both confidence intervals is greater than 0.

**Table 9-3: Assumptions for Proportions of Predictions for Adenomas (Sensitivity, Reference Standard Positive) with CF-HQ190**

		CDSD-unaided Prediction		Total
		Positive	Negative	
CDSD-aided Prediction	Positive	0.8411	0.0859	0.9270
	Negative	0.0365	0.0365	0.073
	Total	0.8776	0.1224	1.00

**Table 9-4: Assumptions for Proportions of Predictions for Adenomas (Sensitivity, Reference Standard Positive) with PCF-H190**

		CDSD-unaided Prediction		Total
		Positive	Negative	
CDSD-aided Prediction	Positive	0.8301	0.0749	0.905
	Negative	0.0475	0.0475	0.095
	Total	0.8776	0.1224	1.00

**Table 9-5: Assumptions for Proportions of Predictions for Non-Adenomas (Specificity, Reference Standard Negative) with CF-HQ190**

		CDSUnaided Prediction		Total
		Positive	Negative	
CDSD-aided Prediction	Positive	0.124	0.124	0.248
	Negative	0.299	0.453	0.752
	Total	0.423	0.577	1.00

**Table 9-6: Assumptions for Proportions of Predictions for Non-Adenomas (Specificity, Reference Standard Negative) with PCF-H190**

		CDSUnaided Prediction		Total
		Positive	Negative	
CDSD-aided Prediction	Positive	0.1415	0.1415	0.283
	Negative	0.2815	0.4355	0.717
	Total	0.423	0.577	1.00

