The diagnosis will be rendered by the pathologist, who is blinded to the endoscopists' polyp characterization, and the pathology report will be reviewed by the endoscopist. A CDSD-aided or CDSD-unaided prediction of Adenoma will be rendered as a True Positive when the pathological diagnosis is 'conventional adenoma' (a.k.a. tubular adenoma), tubulovillous adenoma, villous adenoma, traditional serrated adenoma (TSA), adenoma with high grade dysplasia or cancer. A CDSD-aided or unaided prediction of non-adenoma will be rendered as a True Negative when the pathological diagnosis is hyperplastic polyp, sessile serrated polyp (SSP), inflammatory polyp, lymphoid aggregate/follicle, granulation tissue or normal colonic mucosa. Diminutive polyps that are lost following resection or destroyed during pathology prior to diagnosis will be excluded from the analysis due to lack of ground truth pathology results.

In cases where the CDSD-aided endoscopist prediction and the pathology result differs, a recut and reanalysis of the tissue block will be conducted. In such cases, the second successful pathology reading will be recorded and used as the histopathological ground truth.

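### The endoscopist-then-patient bootstrap, read with replacement at both stages, gives about 61–67% power at 1,918 polyps and 70–76% at 2,400, not the stated 80%; the wording and the power figure disagree

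*Combined protocol and SAP*

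**What the plan says.** The primary decision needs both lower 95% limits, for the aided-minus-unaided differences in sensitivity and specificity, to exceed 0. Section 9.1.1.3 says these intervals are "estimated using bootstrap resampling with resampling performed first at the endoscopist level and then at the patient level". The synopsis (Statistical Test Method) says the same.

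For the planning simulation, section 9.1.1.3 repeats the scheme: "Bootstrap resampling is performed first at the endoscopist level and then at the patient level". It then defines power: "The power is calculated as the number of simulation steps where the lower bound of both confidence intervals is greater than 0". Section 9.1.1.2 gives the result: "In order to demonstrate the primary endpoint with 80% power and one-sided significance level of 2.5% a minimum of 40 endoscopists" and about 2,400 subjects, yielding at least 1,918 polyps. Assumption 1 in section 9.1.1.3 adds that "each endoscopist makes approximately 60 predictions", which for 40 endoscopists is 2,400 predictions.

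The text does not state replacement at either stage, the type of bootstrap interval or the number of resamples. The distribution of adenomas within subjects "was modelled and is described in the statistical analysis plan"; that description is not in the text supplied.

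**The concern.** Drawing as many patients as an endoscopist has, without replacement, returns the same patients. For the patient stage to do anything, it must be drawn with replacement. But the endoscopist stage already carries the patient-level noise, because each endoscopist's observed result contains it. A second draw adds that noise again, and the interval becomes too wide.

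The error is on the safe side for false positives. The cost is power. If the analysis follows the text on this reading, a device performing exactly as assumed misses the co-primary endpoint about 33–39% of the time at 1,918 polyps, or about 24–30% at 2,400, against the 20% implied. Two analysts could also compute different primary intervals from the same data, with standard errors differing by about a quarter.

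**Working it through.** **Inputs.** From sections 9.1.1.2 and 9.1.1.3: 40 endoscopists; 58% adenomas; endoscopes split 50/50; intra-cluster correlation 0.05 per endoscope and polyp class, with none across endoscopes; Dirichlet cell probabilities; prediction rates 89% and 84%; cells from Tables 9-3 to 9-6.

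**Polyp count.** 2,400 × 0.85 × 0.52 × 1.81 = 1,920, in line with the plan's 1,918.

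**Sensitivity, normal approximation at 1,918 polyps, tables applied to all polyps.**

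- Adenomas: 1,918 × 0.58 = 1,112. Per endoscopist and endoscope: 1,112/80 = 13.9.
- Differences: 0.0859 − 0.0365 = 0.0494 (CF-HQ190) and 0.0749 − 0.0475 = 0.0274 (PCF-H190); mean 0.0384.
- Variance per polyp (discordance minus squared difference): 0.1224 − 0.0494² and 0.1224 − 0.0274²; mean 0.1208.
- True design effect: 1 + 12.9 × 0.05 = 1.645. SE = √(0.1208 × 1.645/1,112) = 0.0134.
- A second draw with replacement adds the within-endoscopist share, 1 − 0.05 = 0.95: 1.645 + 0.95 = 2.595. Bootstrap SE = √(0.1208 × 2.595/1,112) = 0.0168. Ratio 1.26.
- Power, patients kept whole: Φ((0.0384 − 1.96 × 0.0134)/0.0134) = Φ(0.91) = 0.82. This reproduces the plan's figure.
- Power, both stages with replacement: Φ((0.0384 − 1.96 × 0.0168)/0.0134) = Φ(0.41) = 0.66.

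**The same at 2,400 predictions.** 1,392 adenomas, 17.4 per endoscopist and endoscope; factors 1.82 and 2.77; SEs 0.0126 and 0.0155. Power is 0.86 with patients whole and 0.74 with two stages.

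**Specificity at 1,918 polyps.** 806 non-adenomas, mean difference 0.1575, factors 1.454 and 2.404, SEs 0.0268 and 0.0344. Two-stage power exceeds 0.99, so sensitivity drives the shortfall. In the simulations below specificity power was at least 0.98.

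**Simulation of joint power.** Two independent simulations used percentile limits, 500–600 resamples and 2,000–4,000 trials per cell (Monte Carlo error about 1 point). The within-patient model is an assumption: a mean of 1.81 polyps per patient, with no added within-patient correlation in accuracy.

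| Polyps and handling | Two-stage | Patients whole |
|---|---|---|
| 1,918, tables applied to all | 0.65; 0.66 | 0.82; 0.81 |
| 1,918, no-prediction set to aided = unaided | 0.62; 0.615 | 0.79; 0.78 |
| 1,918, no-prediction dropped | 0.63; 0.62 | 0.79; 0.79 |
| 1,918, no-prediction and normal non-adenomas dropped | 0.61 | 0.79 |
| 2,400, range over handlings | 0.70–0.74 | 0.83–0.86 |

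A smaller further check (800–1,000 trials per cell) gave 0.67 against 0.82 at 1,918, and 0.65 against 0.81 with aided = unaided for no-prediction polyps. Taking the checks together, two-stage power at 2,400 was about 0.70–0.76. Geometric polyp counts (0.66) or adenoma status clustered within patients (0.66–0.67) changed little.

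**One-sided error on sensitivity** (4,000 trials, nominal 2.5%): two-stage 0.5–1.0%. With patients whole: percentile limits 2.8–3.0% (3.3–3.4% in a smaller run of 2,000 trials), and limits using t with 39 degrees of freedom 2.1–2.5%.

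**What would bring two-stage sampling to about 80%.** Only a change to a stated input did so: a 90% interval (78%, sensitivity alone), an intra-cluster correlation near 0 (81.5%), or about 2,800–3,000 polyps (79.2% at 2,806; 79.7% at 2,986).

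**The case against.** The strongest objection is that the text never says patients are drawn with replacement. The patients-whole runs land on the stated 80%, which suggests loose wording at least as much as an underpowered trial, and a statistical analysis plan with more simulation detail is cited. This stands, and it limits the claim. A reader might infer that the trial is underpowered or that 80% is a miscalculation; the documents do not support that, because they do not rule out a program that kept patients whole.

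Second, 1,918 is a minimum, and assumption 1 implies 2,400 predictions. This also stands, so both counts are given. It narrows the gap without closing it.

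Third, a conservative interval adopted after agency feedback (Revision History) is defensible, and the risk falls on the sponsor. That is true of validity, but a conservative rule still needs a power figure that belongs to it.

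A stronger reading concerns normal tissue. Assumption 11 gives the share of predictions "assessed as normal tissue by pathology is estimated to be approximately 15" per cent. Taking these polyps out before applying the 58% prevalence would cut adenomas from 1,112 to 946 and two-stage power at 1,918 to about 54–61%. That is not the natural reading. Section 5 lists "granulation tissue or normal colonic mucosa" among the non-adenoma diagnoses, and assumption 10 calls 58% the overall adenoma prevalence, so normal tissue sits within the other 42%. That removal would also lower power with patients whole, so it does not explain the disagreement.

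**Conclusion.** The concern holds as an inconsistency between the described procedure and the stated power. With replacement at both stages, the sensitivity SE is inflated by about 25%. Joint power is then about 61–67% at 1,918 polyps and about 70–76% at 2,400. With patients carried whole it is about 79–82% at 1,918. The gap of roughly 15–18 points at 1,918 is far larger than simulation error.

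This rests on the ordinary but unstated reading of the patient stage, the plan's own inputs, and an assumed within-patient model to which the results proved insensitive. A reader might also suspect an inflated false-positive rate. The two-stage interval does the opposite, and a positive result under it remains valid. The point should be fixed, with medium confidence about which side of the disagreement is at fault.

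**What to change.** 1. Check which algorithm the planning simulation used, and use that same algorithm for the primary analysis.
2. If patients were kept whole, correct the synopsis and both statements in section 9.1.1.3 to say that only endoscopists are resampled, each carrying all their patients and polyps. Check the one-sided error with 40 clusters, because percentile limits ran slightly liberal at about 3%.
3. If both stages were drawn with replacement, rerun the simulation and restate the power. The figures here rest on an assumed within-patient model and should not be copied into the protocol. Keeping that rule and 80% power would take about 2,800–3,000 polyps, roughly 46–56% above 1,918, with the tables applied to all polyps, and more otherwise.
4. In either case state replacement at each stage, interval type, number of resamples, and whether 1,918 or 2,400 predictions were simulated. As a side note, say how no-prediction polyps and the 15% normal tissue enter the simulation.

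Cost: a check of one program and wording in three places, with a rerun only under item 3. The Revision History lists the bootstrap and the sample size re-calculation as agency feedback, so confirm any change of rule, as opposed to a correction of its description, with the agency first.

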### 5 Study Design

The study shall be a prospective, single arm, multicenter study. Endoscopists comprising a range of clinical experience will be invited to participate in the study at each site. All

participating endoscopists will receive an overview of the NICE classification to guide their unaided and CDSD-aided assessments as well as instruction on the use of CDSD.

For each participating endoscopist, consecutive subjects presenting for colonoscopy and meeting the pre-procedure entrance criteria will be consented and screened. Consented subjects meeting all the entrance criteria will be enrolled and undergo colonoscopy per the standard of care with the added use of CDSD. CDSD-unaided and CDSD-aided predictions will be compared with the ground truth of histopathology. Presuming at least 40 endoscopists participate, each endoscopist will make approximately 60 predictions on diminutive polyps through the course of the study.

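### The plan states about 60 diminutive-polyp predictions per endoscopist, but its own yield factors and 1,918-polyp target give 48, so it is unclear which count the 80% power was simulated for

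*Combined protocol and SAP*

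**What the plan says.** Two places give a workload per endoscopist. Section 5 says that, with at least 40 endoscopists, "each endoscopist will make approximately 60 predictions on diminutive polyps through the course of the study". Section 9.1.1.3, assumption 1, repeats it: "There are at a minimum 40 endoscopists participating in the study and each endoscopist makes approximately 60 predictions".

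Other places give a polyp total. Section 9.1.1.2 states that for 80% power at one-sided 2.5%, "a minimum of 40 endoscopists and approximately 2400 subjects are required". It then applies 85% adequate bowel preparation, 52% of those subjects with at least one diminutive polyp, and 1.81 polyps per such subject, which "yields a minimum requirement of 1918 polyps". The synopsis and section 5.1 give the same pair, 2,400 subjects and 1,918 polyps. Assumption 10 lists the yield factors again, beginning "The proportion of subjects that present with adequate bowel preparation will be 85" (a percentage).

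On how the power was obtained, section 9.1.1.3 says: "A simulation analysis was performed in which a dataset is generated at each step following the assumptions above". On the interval method it adds: "Bootstrap resampling is performed first at the endoscopist level and then at the patient level".

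**The concern.** Assumption 1 and assumption 10 are both listed inputs to the simulation behind the sample size. At 2,400 subjects and 40 endoscopists they imply different numbers of polyps, and nothing in the text says how many polyps per endoscopist were generated.

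If about 48 were generated, the 60 is only a wrong label. If 60 were generated, the 80% power belongs to a trial of about 2,400 polyps, and the power at the 1,918 actually targeted is lower than stated. As written, the power calculation cannot be traced or reproduced.

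**Working it through.** **Polyp yield (factors from section 9.1.1.2 and assumption 10)**

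- Subjects with diminutive polyps: 2,400 × 0.85 × 0.52 = 1,060.8.
- Polyps: 1,060.8 × 1.81 = 1,920. The plan prints 1,918. Truncating at each step gives exactly that: 1,060 × 1.81 = 1,918.6, cut to 1,918. The plan's total is reproduced.
- Per endoscopist: 1,918 / 40 = 47.95, so about 48.

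**The stated workload (section 5 and assumption 1)**

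- 40 × 60 = 2,400 polyps, and 2,400 / 1,918 = 1.25.
- Subjects needed for 2,400 polyps at the plan's yield: 2,400 / (0.85 × 0.52 × 1.81) = 3,000.

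**Readings that might rescue 60 as a polyp count**

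| Reading | Result |
|---|---|
| Two predictions per polyp (NBI and aided) | 96 |
| Three predictions per polyp (adding white light) | 144 |
| Only polyps with a device prediction (mean of 89% and 84% = 86.5%) | 48 × 0.865 = 41.5 |
| Excluding 15% normal tissue | 48 × 0.85 = 40.8 |
| Fewer endoscopists | 1,918 / 60 = 32, below the minimum of 40 |
| Leaving out the 85% factor | 2,400 × 0.52 × 1.81 = 2,259; / 40 = 56.5 |
| Subjects per endoscopist | 2,400 / 40 = 60 |

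Only the last gives 60 exactly, and it counts subjects, not polyps. The row above it comes close, but its total is 2,259 and not 1,918. The synopsis (Sample Size Parameters) lists its factors without the 85%, so those factors multiply to 2,259 although it prints 1,918.

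**Size of the gap by formula**

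Sensitivity drives the joint power; specificity power is above 99.9% by this formula at either count.

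- Mean sensitivity gain from Tables 9-3 and 9-4: [(0.0859 − 0.0365) + (0.0749 − 0.0475)] / 2 = 0.0384.
- Discordance in each table: 0.1224. Per-polyp variance is discordance minus squared difference, averaging about 0.1208.
- Design effect: 1 + (m − 1) × 0.05, where m is adenomas per endoscopist and scope, with an even scope split within each endoscopist assumed. SE = √(0.1208 × design effect / adenomas). Power = Φ(0.0384 / SE − 1.96).

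| | 1,918 polyps | 2,400 polyps |
|---|---|---|
| Adenomas (58%) | 1,112 | 1,392 |
| m = adenomas / 80 | 13.9 | 17.4 |
| Design effect | 1.645 | 1.82 |
| SE | 0.0134 | 0.0126 |
| Joint power | 81.9% | 86.3% |

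**Size of the gap with the planned resampling**

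Cell probabilities were drawn per endoscopist, scope and polyp class from a Dirichlet distribution centred on Tables 9-3 to 9-6, with parameter sum 1/0.05 − 1 = 19. There were 26.5 or 33.1 subjects with polyps per endoscopist, and scope was drawn 50:50 per subject. Endoscopists and then patients were resampled, 500 draws per trial, 4,000 trials per count. Three choices had to be assumed: 1 + Poisson(0.81) polyps per subject, independent histology within subject, and percentile intervals.

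- Two-stage bootstrap: 65.9% at 1,918 against 74.5% at 2,400, a gap of 8.6 points. Monte Carlo SEs are 0.75 and 0.69 points, so the 95% error of the gap is about ±2 points.
- Assumed within-subject histology correlation of 0.2: 65.9% against 74.4%. Of 0.4: 65.0% against 74.4%.
- Endoscopists only resampled, same trials: 81.6% against 86.4%, in agreement with the formula.

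A separate run with a zero-truncated Poisson for polyps per subject gave about 64–68% against 74–76% for the two-stage method. With endoscopists only resampled, and the aided call set equal to the unaided call when the device gave no prediction, it gave 79.5% against 83.1%.

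**The case against.** The strongest reply is that the 60 is a mislabelled count of subjects. Every operative statement agrees on 2,400 subjects and 1,918 polyps, and the 80% power is tied to 2,400 subjects and 40 endoscopists. A simulation that resamples patients has to generate patients, and the 85% factor has a purpose only if generation starts from enrolled subjects. The formula at 1,918 also lands near 80%. On this view the remedy is a change of wording in two sentences. The simulated count may also be given in the analysis-plan text to which assumption 5 refers, which says that "The distribution of adenomas and non-adenomas within subjects with more than one diminutive polyp was modelled" but whose model is not shown in the text available here.

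Much of this stands. It is the most natural reading, and nothing outside the two sentences that give 60 supports a simulation of 2,400 polyps. It remains an inference, because section 5 explicitly counts predictions on diminutive polyps. The power figures do not settle it either: the formula at 1,918 comes close to 80%, but under the planned two-stage resampling neither count reaches 80% in the assumed models, and 2,400 is the nearer.

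The caution about the two-stage levels also stands. They rest on a within-subject model that had to be assumed, and the main runs do not model no-prediction or normal-tissue handling separately. They should not be read as evidence that the trial is underpowered.

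**Conclusion.** The contradiction holds with high confidence and needs only multiplication: 60 against 48 predictions per endoscopist, 2,400 against 1,918 polyps, a 25% difference that an approximate figure does not cover. It should be corrected because assumption 1 is a stated input to the power simulation.

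Which count was simulated cannot be determined from the text. The choice is worth roughly 4 to 9 points of joint power, depending on the model: about 4 by formula with an even scope split, and about 9 with two-stage resampling under the assumptions above. The 80% claim is neither confirmed nor refuted. The omission of the 85% factor from the synopsis is a minor inconsistency, since section 9 states it.

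**What to change.** 1. Check the simulation inputs and state in section 9.1.1.3 how many polyps in total, and per endoscopist, were generated.
2. If the total was about 1,918, change 60 to about 48 in sections 5 and 9.1.1.3, or relabel it as 60 subjects per endoscopist.
3. If it was about 2,400, re-run the planned two-stage bootstrap simulation at 1,918 and restate the power. The sponsor would then have to accept the lower figure or revisit the sample size.
4. Add the 85% bowel-preparation factor to the synopsis.

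The cost is a look at the simulation inputs and edits in three places. A simulation re-run is needed only in the third case.
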